demonstrates the minimum detectable change in the False Positive Rate (ΔFPR). The FPR is the number of False Positives divided by the false positives plus the True Negatives ($\text{FPR} = ((\text{FP})/(\text{FP}+\text{TN}))$). Additionally, the $\text{FPR} = 1 - \text{Specificity}$ and perhaps more importantly, ΔFPR is

Table 2 - Detectable change in the Percentage of cases classified as high risk by adding biomarkers to the clinical model.					
Total Sample Size	Event Rate	Expected Number of AKI Progressors (Cases)	10% Classified as High Risk without biomarker	20% Classified as High Risk without Biomarker	50% Classified as High risk Without biomarker
150	15%	22.5	0.21	0.30	0.36
150	30%	45	0.16	0.20	0.26
150	45%	67.5	0.13	0.17	0.22
200	15%	30	0.20	0.28	0.34
200	30%	60	0.15	0.19	0.25
200	45%	90	0.12	0.16	0.20
250	15%	37.5	0.19	0.26	0.32
250	30%	75	0.14	0.18	0.23
250	45%	112.5	0.11	0.15	0.19
300	15%	45	0.18	0.24	0.30
300	30%	90	0.13	0.17	0.21
300	45%	135	0.10	0.14	0.17

equivalent to the NRI
Non Event (non-
progression to Stage 3).
Thus one could look at
Table 6 and view these
numbers as the NRI for
Non-Events.

For the
purpose of this
analysis we have
varied the cohort
sample size as well as
the event rate
(progression). Event
rate variation accounts
for the limited data on
progressive AKI in the

existing literature. While our pilot data (n=77) demonstrated an event rate 32% [11], previously published studies have had varied rates from TRIBE AKI's (13%) [16], EARLY-ARF's (33%) [17] and Siew's et al (29%) [18]. As such a rate progression rate of 30% seems appropriate. To interpret Table 2 if we assume we have 200 individuals with a 30% AKI progression rate (60 cases /AKI progressors) we will be able to detect improvements of 0.15-0.25 in the % of cases classified as high risk (Δ TPR=NRI events). Inversely, for the same cohort and event rate we would be able to detect identical improvements in the Δ FPR (= NRI for non-events). **Thus with 200 subjects and a 30% event rate we would be able to detect small to medium sized improvements in reclassification (NRI events + NRI non-events =Total NRI 0.30-0.50)[19]**

Endpoints and Definitions

AKI – an increase in serum creatinine of >0.3 mg/dL or 50% increase from baseline over 48 hours or an increase to greater than or equal to 150 to 200 percent from baseline or sustained oliguria (mean output of <0.5 cc/kg/hr for 6 hours).

Non-renal recovery

- (1) Patients who require RRT within 14d of enrollment

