- (2) Patients who die before 14d, and whose serum creatinine remains >2.0 mg/dl over baseline creatinine at the time of death
- (3) Patients who die before 14d and whose urine output is less than 400cc/24 hours at the time of death

Renal Recovery

- (1) Patients who do not require RRT and survive 14d or are discharged prior to 14 days
- (2) Patients who die before 14d with a serum creatinine >2.0 mg/dl above their baseline AND with a urine output >400cc/24 hours

Statistical Analysis

Patients will be followed for 30 days or until hospital discharge, whichever occurs first. Need for dialysis, serum creatinine, urine output, medication regimens, and mortality will be assessed. Primary analysis will be based on the net reclassification index as discussed in the sample size section above, additionally we will look at the more traditional receiver operating characteristics (ROC) of urine output and urinary sediment score and biomarkers after furosemide challenge to predict AKI progression. Additionally, time to AKI progression and renal recovery/non-recovery will be assessed. Patient outcomes will be stratified by entry criteria and baseline renal function. We will be looking at the long term, (3 year) outcomes in this cohort as well. However given the focus of this study is to identify severe AKI early in the clinical course and that rates of morbidity and mortality in our ICU- AKI cohort are extremely high, we are not sufficiently powered to look at long term outcomes and this aspect of the study is somewhat exploratory and will serve as pilot data for future studies.

Study Procedures

1. Identify appropriate patients via inclusion/exclusion
2. Consent patient or legal representative
3. Draw 7cc of blood, collect 50cc of fresh urine
4. Bolus dose of furosemide
5. Assess urine output response over the next 6 hours
6. Match urine output with intravenous isotonic saline, 1 ml for 1 ml for 6 hours (at the discretion of the clinically treating team – if they feel diuresis is needed clinically they can decide to hold the intravenous fluids – this has not changed from prior submission)
7. Draw 7cc of blood, collect 50cc of fresh urine 2 hours after the furosemide
8. Draw 7 cc of blood; and another 50cc of urine the following morning at 24 hours post dose
9. Draw 7 cc of blood; and another 50cc of urine at the time of ICU discharge
10. Draw 7 cc of blood; and another 50cc of urine at the time of hospital discharge

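### The 14-day recovery and non-recovery definitions overlap for one type of death before day 14 and leave another type with no code

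*Combined protocol and SAP*

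**What the plan says.** The rules are in the combined protocol and SAP, section D, Endpoints and Definitions.

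Non-renal recovery has three items:
- Item 1: "Patients who require RRT within 14d of enrollment".
- Item 2: "Patients who die before 14d, and whose serum creatinine remains >2.0 mg/dl over baseline creatinine at the time of death".
- Item 3: "Patients who die before 14d and whose urine output is less than 400cc/24 hours at the time of death".

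Renal recovery has two items:
- Item 1: "Patients who do not require RRT and survive 14d or are discharged prior to 14 days".
- Item 2: "Patients who die before 14d with a serum creatinine >2.0 mg/dl above their baseline AND with a urine output >400cc/24 hours".

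The Statistical Analysis section puts the outcome to use: "Additionally, time to AKI progression and renal recovery/non-recovery will be assessed". That sentence leaves open whether recovery is to be a time-to-event analysis. The same section says "Patients will be followed for 30 days or until hospital discharge, whichever occurs first", and it lists the components separately: "Need for dialysis, serum creatinine, urine output, medication regimens, and mortality will be assessed". After discharge, outside laboratory results are still sought (Long Term Follow-up; Study Procedures, items 11 to 13). The plan gives no order of precedence among the five items and no category for patients who meet none of them.

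**The concern.** A two-category outcome needs rules that give each patient exactly one code. Here the two rules for death with raised creatinine use the same inequality in the same direction, and only the recovery rule adds a urine-output condition. With values taken at death, every patient who meets Renal Recovery item 2 also meets Non-renal recovery item 2. The recovery rule therefore never identifies a death that counts as recovery only. The death with the better kidney status on both measures is the one left without a code.

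Followed as written, the classification of non-oliguric early deaths depends on a coding choice that the plan does not state. These deaths are defined partly by urine output, and the test under study is urine output after furosemide. The choice could therefore be related to the predictor; that is an inference, not something the documents say. The plan describes mortality in this cohort as extremely high, so early deaths cannot be set aside as a remote case.

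**Working it through.** No sample-size or power figure is involved, so the check is to apply the five rules to every type of death before day 14.

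**Inputs.** The five items quoted above, with cut-offs of 2.0 mg/dl and 400 cc/24 h. Any RRT in a patient who dies before day 14 falls within the 14-day window. Creatinine and urine output are taken at the time of death.

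**In-hospital deaths.** RRT (2 levels) × creatinine rise (2) × urine output (3) = 12 cells.

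| RRT | Creatinine rise (mg/dl) | Urine output (cc/24 h) | Non-recovery items met | Recovery items met | Code |
|---|---|---|---|---|---|
| No | ≤2.0 | <400 | 3 | none | non-recovery |
| No | ≤2.0 | exactly 400 | none | none | **no code** |
| No | ≤2.0 | >400 | none | none | **no code** |
| No | >2.0 | <400 | 2, 3 | none | non-recovery |
| No | >2.0 | exactly 400 | 2 | none | non-recovery |
| No | >2.0 | >400 | 2 | 2 | **both** |
| Yes | >2.0 | >400 | 1, 2 | 2 | **both** |
| Yes | other five cells | | 1, with or without 2 and 3 | none | non-recovery |

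This gives 2 cells coded both ways and 2 uncoded. Setting aside the boundary at exactly 400, the four main cells without RRT contain one double code and one gap, and the four with RRT contain one double code.

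**Timing.** Renal Recovery item 2 does not say that its values are those at death, whereas Non-renal recovery items 2 and 3 do. If its creatinine could be a value from any time, deaths above 2.0 at death still overlap, and deaths that never exceeded 2.0 with output above 400 still have no code.

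**Deaths after discharge but before day 14 (secondary).** Renal Recovery item 1 has two readings:
- Reading A: no RRT, and either survival or discharge.
- Reading B: either no RRT with survival, or discharge.

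Without RRT, item 1 makes all six cells recovery. Four of them also meet Non-renal recovery item 2 or 3 if values at death are obtained. With RRT, reading A double-codes one cell and reading B double-codes all six. The totals over 24 cells are:
- Reading A: 2 + 4 + 1 = 7 both, 2 uncoded.
- Reading B: 2 + 4 + 6 = 12 both, 2 uncoded.

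These totals count cells, not patients, and do not measure seriousness.

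**Would reversing the sign in Renal Recovery item 2 be enough?** No. With the rise changed to 2.0 or less and nothing else altered, the in-hospital double code and the main gap without RRT are resolved. However, RRT deaths at ≤2.0 and >400 become double-coded, and exactly 400 cc with a rise ≤2.0 stays uncoded.

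**After the changes set out under the fix.**
- Changes 1 and 3 only: 0 both under reading A, 6 both under reading B, none uncoded.
- Changes 1 and 2 only: 4 both, none uncoded.
- All three: 0 both and 0 uncoded, with 16 cells non-recovery and 8 recovery.

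**The case against.** The strongest reply is about weight. The main fault looks like a single reversed sign, and a symbol misread when the PDF was converted to text cannot be excluded, although nothing shows one. The outcome occupies half a sentence of the analysis section, with no model, test or power attached. Dialysis and mortality stay separately reportable. The cell counts say nothing about how many patients are involved. All of this stands and limits the importance of the point. It does not remove the fault, because even with the sign reversed the missing RRT exclusion and the boundary at 400 cc remain.

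The secondary points are weaker, and fairly criticised:
- Reading B would also place RRT patients discharged alive before day 14 in both lists, so it is unlikely to be intended. The ambiguity is still cheap to remove.
- The overlap after discharge needs values at death. In-hospital follow-up has ended by then, 24-hour urine output is not among the outside data listed, and the first scheduled call is at day 30. It is therefore largely hypothetical, and most so for the urine-output rule.

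Two further gaps are fair observations but separate from this one. Renal Recovery item 1 sets no time window for RRT, so a patient who first needs it after day 14 is not clearly in either list. Section A also names recovery after dialysis as a possible course, whereas the definitions count all RRT within 14 days as non-recovery.

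**Conclusion.** The concern holds. For in-hospital deaths before day 14 without RRT, two of the four main creatinine-by-urine-output cells are faulty: one is coded both ways and one has no code. One of the four matching RRT cells is coded both ways. This follows directly from the wording and does not depend on how Renal Recovery item 1 is read.

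The number of patients affected cannot be computed, since the documents give no rate of death before day 14 by RRT, creatinine and urine output. The damage is confined to the additional recovery/non-recovery analysis. The primary net reclassification analysis, the ROC analyses and the sample size of 200 rest on AKI progression and are not touched. That the sign in Renal Recovery item 2 is reversed is a plausible explanation which the documents do not confirm. The definitions should be corrected before this outcome is analysed.

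**What to change.** Subject to the sponsor confirming what was intended, including the boundary values, amend the definitions as follows. The plan's own cut-offs are kept.

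1. **Renal Recovery item 2:** restrict it to patients who had no RRT and died before day 14 with, at the time of death, creatinine at most 2.0 mg/dl above baseline and urine output of 400 cc/24 h or more. This is four edits in one: the direction of the inequality, the RRT exclusion, the timing of the values (to match the non-recovery items), and the inclusion of exactly 400 cc.
2. **Renal Recovery item 1:** reword so that absence of RRT applies to both branches, that is, no RRT together with either survival to day 14 or earlier discharge.
3. **Deaths after discharge but before day 14:** state one category. One way is to limit the three death-based rules (Non-renal recovery items 2 and 3, Renal Recovery item 2) to in-hospital deaths.

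With all three, every death before day 14 has exactly one code. In the same amendment the sponsor could settle the RRT window in Renal Recovery item 1 and reconcile the definitions with the courses listed in section A.

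The cost is a wording amendment and recoding of data already collected. No extra patients, visits or procedures are needed.

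### If time to renal recovery is meant as a time-to-event analysis, the plan's 14-day recovery status gives it no kidney event to date

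*Combined protocol and SAP*

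**What the plan says.** Section D, Statistical Analysis, after naming the net reclassification index as primary and adding ROC analyses, states: "Additionally, time to AKI progression and renal recovery/non-recovery will be assessed". It gives no time origin, recovery date, censoring rule, handling of competing events or method for this analysis.

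The only definitions are in section D, Endpoints and Definitions. For reference below:

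- **R1**, renal recovery (1): "Patients who do not require RRT and survive 14d or are discharged prior to 14 days"
- **R2**, renal recovery (2): "Patients who die before 14d with a serum creatinine >2.0 mg/dl above their baseline AND with a urine output >400cc/24 hours"
- **N1**, non-recovery (1): "Patients who require RRT within 14d of enrollment"
- **N2**, non-recovery (2): "Patients who die before 14d, and whose serum creatinine remains >2.0 mg/dl over baseline creatinine at the time of death"
- **N3**, non-recovery (3): "Patients who die before 14d and whose urine output is less than 400cc/24 hours at the time of death"

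In-hospital observation runs on a different clock: "Patients will be followed for 30 days or until hospital discharge, whichever occurs first". The data that could date a recovery are listed ("Need for dialysis, serum creatinine, urine output, medication regimens, and mortality will be assessed"), but no threshold or measurement schedule turns them into a recovery date. Section A, Specific Aims, separates recovery without dialysis, recovery after dialysis, dialysis without recovery, and death.

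**The concern.** A time-to-event analysis needs an event that happens on a day. R1 has no creatinine or urine-output criterion, and R2 uses those values only to classify a death. If the analyst applies these rules to time, the clock stops at discharge, at day 14 or at death, and not when the kidney recovers. The result would largely describe length of stay, and some deaths would enter as favourable events. If the analyst instead devises a recovery date later, that choice is made with the data in hand. Either way, the study could not report when recovery occurs, although clinical course is its stated goal.

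**Working it through.** **1. Classify every patient type.** Cross RRT within 14 days (yes/no), fate (alive at day 14, discharged earlier, died before day 14), creatinine (up to 2.0, or more than 2.0 mg/dl, over baseline) and urine output (below or above 400 cc/24 h). This gives 2 × 3 × 2 × 2 = 24 cells. R1 is read as no RRT together with either survival to day 14 or earlier discharge.

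| RRT | Fate | Creatinine over baseline; urine output | Cells | Rules met | Dates supplied |
|---|---|---|---|---|---|
| No | Alive at day 14, or discharged | Any | 8 | R1 | Discharge or day 14 |
| No | Died | ≤2.0; <400 | 1 | N3 | Death |
| No | Died | ≤2.0; >400 | 1 | None | None |
| No | Died | >2.0; <400 | 1 | N2, N3 | Death |
| No | Died | >2.0; >400 | 1 | N2 and R2 | Death |
| Yes | Died | >2.0; >400 | 1 | N1, N2 and R2 | Start of RRT, or death |
| Yes | All others | Any other | 11 | N1 (some deaths also N2, N3) | Start of RRT (deaths under N2 or N3: also death) |

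Totals: recovery only 8; non-recovery only 1 + 1 + 11 = 13; both 2; neither 1. The sum is 24.

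**2. Read off the dates.** All 8 recovery-only cells hold whatever the creatinine or urine output, and their date is min(discharge day, 14). The other two recovery cells are deaths, and the same deaths also meet a non-recovery rule. Only N1 supplies a clinical renal event with its own date, the start of RRT.

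**3. Two patients without RRT.** One has normal creatinine from day 3 but stays in hospital for other reasons: dated day 14. Another goes home on day 4 with creatinine still raised: dated day 4. The order is the reverse of the kidneys' order.

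**4. Illustration of size.** The plan states no figure to reproduce and no distribution of stay. Assume a lognormal stay with median m and log SD 0.6, and ignore death and RRT. The share tied at day 14 is 1 − Φ(ln(14/m)/0.6), and the median assigned time is min(m, 14).

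| Median stay m (days) | ln(14/m)/0.6 | Tied at day 14 | Median assigned time (days) |
|---|---|---|---|
| 7 | 1.155 | 12% | 7 |
| 8 | 0.933 | 18% | 8 |
| 10 | 0.561 | 29% | 10 |
| 12 | 0.257 | 40% | 12 |
| 14 | 0 | 50% | 14 |
| 18 | −0.419 | 66% | 14 |

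No recovery time enters these formulas, because none enters R1. The percentages show the mechanism; they are not estimates for this study.

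**The case against.** The strongest reply is grammatical. The sentence can be read as time to AKI progression, plus recovery/non-recovery as a separate two-class status matching the definitions above it. Non-recovery is also an odd time-to-event outcome. On that reading there is no dating problem. This stands as a real ambiguity, and it makes the point conditional. It does not remove the point: the words for time naturally govern both items, and the plan does not settle which is meant.

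A reader might infer more than the documents support:

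- *That the plan assigns discharge, day 14 or death as the recovery time.* It does not. It is silent, and these are merely the only dates its definitions supply.
- *That a comparison of recovery time by furosemide response is planned and would be biased.* No such comparison is stated for this outcome. The only grouping named is stratification by entry criteria and baseline renal function.
- *That the assigned time would carry no information about the kidney.* That needs stay and recovery to be independent. Recovery plausibly influences discharge, and the documents do not address it.

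It is also fair to say that this is an additional analysis on which nothing is powered.

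**Conclusion.** The concern holds conditionally. If a time-to-event analysis of recovery is intended, the definition cannot supply its event date. Used as written, it would track length of stay truncated at day 14 and would count some deaths as recoveries. This follows from the wording alone and needs no distributional assumption; the tied shares of 12% to 66% depend wholly on the assumed stay.

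A reader might infer that the main result is compromised. It is not: the primary net reclassification analysis concerns progression to Stage 3 and does not use the recovery definition. Nor are the 14-day rules safe as a plain yes/no endpoint in their present form, since two of the 24 cells meet both classes and one meets neither. The correction is worth making before analysis but is not critical to the trial.

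**What to change.** 1. **State the outcome type.** Say whether recovery/non-recovery is a yes/no or a time-to-event outcome. If yes/no, one sentence and item 3 suffice.
2. **If time-to-event, define a dated event from data already assessed.**
   - Time origin: enrollment.
   - Event: the first day, alive and off RRT, on which the patient no longer meets the AKI criterion under which they entered, confirmed on the next value where one exists. Use creatinine for creatinine entrants and urine output for those who entered on oliguria alone. Express creatinine relative to baseline, because a 48-hour change would let a high plateau pass as recovery.
   - For oliguria entrants, say how urine output in the six hours after the bolus is treated, since a diuretic response could otherwise be dated as recovery.
   - Death: a competing event, reported by cumulative incidence.
   - Discharge before recovery: end of observation, not recovery, with a sensitivity analysis because discharge may be informative.
   - RRT: report recovery without RRT (RRT as a competing event) separately from recovery after RRT, to match the outcomes in Specific Aims.
3. **Reconcile the death-based rules before keeping a 14-day yes/no endpoint.** Death with creatinine more than 2.0 mg/dl over baseline and urine output above 400 cc/24 h meets both R2 and N2. Death without RRT, with creatinine not more than 2.0 mg/dl over baseline and urine output above 400 cc/24 h, meets neither class.

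The cost is SAP wording, with no new data collection. The downside is that recovery dates will be only as precise as the frequency of clinical creatinine and urine-output values, for which the plan sets no schedule.
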